Urine samples were collected using a standardized protocol (Lithotest®, Biohealth, Turin, Italy), and the metabolic profile was examined in an external certified lab (Lithocenter, Turin, Italy). Briefly, during collection, 24-hour (24 h) urine was aliquoted into two fractions to which 10 mL hydrochloric acid (to prevent calcium/phosphate precipitation) and 1 mL Hibitane (to prevent bacterial contamination) were added. The acidified aliquot was used to quantify calcium (Ca), citrate, magnesium (Mg), oxalate, phosphate (PO₄) and sulphate (SO₄); the Hibitane aliquot was tested for ammonium, chloride (Cl), creatinine, pH, potassium (K), sodium (Na), urea, and urate. In addition, a sample of fasting-morning urine was collected within 2 h after the 24 h collection ended, and was analyzed for citrate, calcium, urate (all expressed as creatinine ratios) and pH. Reference values were established on the basis of the assessment of mineral metabolic profile to evaluate the lithogenic risk [2,3,4]. The renal acid load was determined by calculating the 24 h urinary “potential renal acid load” (uPRAL) as follows [5]:

$$[\text{Cl (mmol day}^{-1}) + \text{SO}_4 \text{ (mmol day}^{-1}) \times 2 + \text{PO}_4 \text{ (mmol day}^{-1}) \times 1.8] - [\text{Na (mmol day}^{-1}) + \text{K (mmol day}^{-1}) + \text{Mg (mmol day}^{-1}) \times 2 + \text{Ca (mmol day}^{-1}) \times 2]$$

5. Immunoenzymatic Assay of BTM

The serum level of the bone turnover markers (BTMs) was evaluated at baseline and after 3 and 6 months of treatment. The BTM assay was carried out by following the recommended actions to minimize the pre-analytical variability [6]. The blood samples were collected after overnight fasting (between 08:00 and 10:00 a.m.), centrifuged within 2 h from collection, at 1000 g min⁻¹ for 15 min and at room temperature. The serum was transferred into cryotubes (0.5 mL of serum per cryotube)

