and frozen at -80°C , within 1 h after centrifugation, until testing. The BTM serum levels were measured using commercially available reagents based on a sandwich enzyme immunoassay technique, following the manufacturer's protocols, with each sample tested in duplicate. The selected BTMs were related to (i) the number of osteoclasts (tartrate-resistant acid phosphatase 5b; TRACP5b); (ii) osteoblast function (bone alkaline phosphatase; BAP); (iii) type I collagen degradation (carboxy-terminal telopeptide; CTX); (iv) type I collagen precursor (procollagen type 1 N terminal propeptide; PINP). Source and technical notes of reagents used in this study are shown in Table 1.

Table 1. Source of the immunoenzymatic assay kits, sensitivity, precision, least significant change (LSC) and references values from healthy individuals.

Marker (Unit) Commercial name (Source)	Detection limit	Min - Max intraassay CV (%)	Min - Max interassay CV (%)	LSC (%)	Mean \pm SEM Median Min - Max		
					Female (postmenopausal)	Female (premenopausal)	Male
CTX ($\mu\text{g} \cdot \text{L}^{-1}$) Serum Crosslaps - (Immunodiagnostic systems Limited, Boldon, UK)	0.02	1.8 - 3.0	2.5 - 10.9	16.6	0.64 \pm 0.36 0.44 0.12-1.35	0.38 \pm 0.19 0.29 0.11-0.74	0.39 \pm 0.19 0.29 0.12-0.75
BAP ($\mu\text{g} \cdot \text{L}^{-1}$) Ostase BAP - (Immunodiagnostic systems Limited)	0.7	2.6 - 6.5	3.7 - 6.1	15.6	14.53 \pm 4.21 13.2 8.0-22.4	9.0 \pm 2.98 8.78 4.0-14.30	13.13 \pm 3.8 12.3 7.0-20.1
PINP ($\text{pg} \cdot \text{L}^{-1}$) Human Procollagen I N-terminal Peptide (Cusabio Technology LLC, Aachen, Germany)	18.75	8	10	29.8	22.6 \pm 1.7 ¹ 20.1 15.4-40.8		
TRACP5b ($\text{U} \cdot \text{L}^{-1}$) Bone TRAP (Immunodiagnostic systems Limited)	0.5	6.0-6.6	5.8-7.2	21.1	3.19 \pm 0.85	2.59 \pm 0.78	3.06 \pm 0.88

¹ Reference values have not been differentiated by gender and age.

6. Calculations and Statistical Analysis

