All calculations and analyses were carried out using StatView 5.01 for Windows (SAS Institute Inc., Cary, NC, USA) and MedCalc Statistical Software version 18.2.1 (MedCalc Software bvba, Ostend, Belgium). The sample size calculation was based on a previous randomized clinical trial (RCT) aimed to evaluate the effect of K citrate on calcium metabolism and BTM in a cohort of individuals (males and females, age >55 years) treated for 6 months [7]. The present RCT was powered considering a Type I error (α) = 0.05 (two-sided), and Type II error (β) = 0.20 (power is 80%). Fifteen patients per group were sufficient, but the expected proportion of dropouts was 20%; therefore, as a precaution, 20 women in each group were recruited. Quantitative data were expressed as the arithmetic mean plus or minus the standard error of the mean (mean \pm SEM). The D'Agostino-Pearson method was used

to test the normality assumption of continuous variables, and a *log* transformation was applied when the data distribution was non-normal. The data analysis was carried out following intention-to-treat principles. All follow-up parameters were analyzed using a “last value carried forward” approach under the intention-to-treat principle in order to address missing data [8]. The effect of K citrate on BTMs and blood/urine analytes was evaluated by applying the *t*-test, with comparison within the groups (paired analysis of the effect of treatment over time), and between the groups (independent comparison between K citrate and the placebo at the same time point). In order to highlight the changes over time, the results were expressed in line-graphs as deviations from the value observed before treatment, i.e., $[(\text{BTM concentration at time point} \times \text{BTM concentration at baseline}^{-1}) - 1]$ Thus, obtaining a baseline value equal to zero. The degree of association between the continuous variables was calculated by measuring the Pearson correlation coefficient. Differences and correlations were considered to be statistically significant when the *p* value was <0.05 .

References

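### Section 6 applies p<0.05 to each of eight between-arm bone-marker tests and names no primary test, so with no marker effect about 13% to 32% of trials would show at least one significant result

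*Combined protocol and SAP*

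**What the plan says.** Section 6 (Calculations and Statistical Analysis) gives one design alpha: "The present RCT was powered considering a Type I error (α) = 0.05 (two-sided"), with 80% power. It finds 15 women per group sufficient, allows for 20% dropout, and continues: "therefore, as a precaution, 20 women in each group were recruited". The calculation rests on a previous trial "aimed to evaluate the effect of K citrate on calcium metabolism and BTM in a cohort of individuals"; no outcome, effect size or standard deviation is given.

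The same section plans t-tests on the BTMs and on the blood and urine analytes. They are run within each arm over time and between arms, the latter described as "independent comparison between K citrate and the placebo at the same time point". The decision rule is common to all of them: "Differences and correlations were considered to be statistically significant when the" p value is below 0.05. On the analysis set it says: "The data analysis was carried out following intention-to-treat principles". Missing follow-up values are filled by carrying the last value forward.

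Section 5 (Immunoenzymatic Assay of BTM) sets the visits: "The serum level of the bone turnover markers (BTMs) was evaluated at baseline and after 3 and 6 months of treatment". It lists four markers (TRACP5b, BAP, CTX, PINP) by the biology that each reflects, beginning "The selected BTMs were related to (i) the number of osteoclasts", and ranks none of them. The text available for review contains no primary outcome, primary visit, test order or multiplicity adjustment.

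**The concern.** A design alpha of 0.05 and a power of 80% have meaning for one identified test, or for a defined family of tests. Here they attach to neither. The source trial covered both calcium metabolism and BTMs, so the text does not show whether the 15 per group rest on a BTM or on a calcium measure.

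Four unranked markers at two unranked visits give eight between-arm comparisons, each judged at 0.05. If K citrate changed none of the markers, the chance that at least one comparison looked significant would be well above 5%. A reader of the analysis section could not tell a planned BTM result from the most favourable of eight.

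**Working it through.** **Inputs from the documents.** Two-sided alpha 0.05, power 80%, 15 per group sufficient, 20% dropout, 20 per group recruited (section 6); 1:1 allocation (opening design section); four BTMs and two post-baseline visits (section 5).

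**Assumed inputs.** Correlation between markers 0 to 0.9; correlation between visits 0.5 to 0.9. The documents give neither.

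**1. The plan's own figure.** 15 / (1 − 0.20) = 18.75, rounded up to 19, so recruiting 20 per group is consistent with the stated dropout. The 15 cannot be reproduced without an effect size. Solving backwards for a two-sample t-test at two-sided 0.05 and 80% power, 15 per group detects a difference of 1.06 SD.

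**2. Count of tests.** 4 markers × 2 visits = 8 between-arm BTM tests. Three groups of tests under the same threshold are left out:
- Within-arm tests, because all women receive vitamin D3 and calcium (section 2), so a change from baseline can be real even if K citrate does nothing.
- Blood and urine analytes, because K citrate would be expected to change urinary potassium and citrate, so a null for all of them is not credible.
- Pearson correlations, which are not comparisons of the arms.

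**3. Independent tests.** Eight tests: 1 − 0.95^8 = 0.337. Four tests: 1 − 0.95^4 = 0.185.

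**4. Correlated tests.** Simulation with no effect on any marker: 20 per arm, eight two-sample t-tests, 100,000 trials per setting. The correlation between different markers at different visits is the product of the marker and visit correlations. Chance of at least one p<0.05:

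| Marker correlation | Visit 0.5 | Visit 0.7 | Visit 0.9 |
|---|---|---|---|
| 0 | 0.320 | 0.297 | 0.256 |
| 0.3 | 0.300 | 0.279 | 0.239 |
| 0.5 | 0.273 | 0.253 | 0.215 |
| 0.7 | 0.228 | 0.212 | 0.180 |
| 0.9 | 0.164 | 0.154 | 0.131 |

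The range is 13% to 32%, or 13/5 = 2.6 to 32/5 = 6.4 times the nominal 5%.

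**5. Sensitivity.**
- 15 per arm: 0.132 to 0.319.
- 4 of 20 women per arm (20%) with the 3-month value carried forward to 6 months: 0.127 to 0.309.
- The four BTMs at 6 months only: about 0.094 (marker correlation 0.9) to 0.186 (correlation 0).

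**6. Does the remedy work?** Chance of any false claim over the four 6-month BTMs, marker correlation 0 to 0.9 (100,000 trials): 0.049 to 0.051 with one BTM as primary and Holm on the other three after it. With Holm on all four it is 0.048 (correlation 0) falling to 0.026 (correlation 0.9).

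**The case against.** The strongest objection is that the premise depends on material not seen. The opening page was not available, and the design section refers to a registry record that was not available either. Either could name a primary outcome and visit. This stands. A reader might infer that the trial has no primary outcome; the documents do not support that. They support only the statement that the text seen names none and that section 6 does not point to one.

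Second, 0.05 per test is a legitimate threshold, and section 6 neither claims a family-wise rate nor says that one significant marker would make the trial positive. This also stands. A reader might infer that the plan promises an overall 5% error rate and then breaks the promise. It does not; there is no internal contradiction. Nor does the rule declare every difference significant: it sets a threshold.

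Third, the range rests on assumed correlations. The 32% end needs uncorrelated markers, and the 13% end needs 0.9 between markers and 0.9 between visits. The exact size is therefore uncertain, and it applies only if no BTM is affected. That the rate exceeds 5% does not depend on the choice, since every setting examined does so, including the 6-month tests alone.

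Finally, in a study of 40 women, reporting all markers unadjusted as exploratory would be defensible. The text seen does not call the study exploratory, though, and it states a design alpha and power.

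**Conclusion.** The point holds as an inexpensive improvement that should be made; it does not show the plan to be invalid. As section 6 is written, alpha and power belong to no identified test. If K citrate affects no BTM, at least one of the eight between-arm BTM tests would reach p<0.05 in about 13% to 32% of trials, and one of the four 6-month tests in about 9% to 19%. These figures assume marker correlations of 0 to 0.9 and, for the eight tests, visit correlations of 0.5 to 0.9. They describe the chance of at least one false result when no marker responds. They are not the probability that a particular reported result is false. If the registry names a primary, what remains is to state it in section 6 and add a rule for the other BTMs.

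**What to change.** In section 6:

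- **If a primary is registered:** state the outcome(s) and visit and test at two-sided 0.05, with Holm if there are several. Claim significance for the non-primary 6-month BTMs only after a significant primary result (all of them, if several), using Holm across however many remain. That is three if the single primary is a 6-month BTM; it is four if the primary is a 3-month BTM or not a BTM.
- **If none is registered and the A/B codes are already broken:** do not name a primary now. Either label all BTM results exploratory, or apply Holm across the four 6-month BTMs and state that this choice was post hoc. Broken codes are likely, since the text is in the past tense and the reference list has a July 2018 access date, but the documents do not say.
- **If none is registered and the codes are intact:** name as primary the 6-month between-arm test of the outcome behind the 15 per group, then follow the first rule for the other BTMs.
- **In every case:** report the other 3-month, within-arm, blood/urine and correlation results as exploratory, with estimates and confidence intervals. A blood or urine measure that is the primary is exempt.

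**Cost.** Wording and analysis only; no new data. A single primary keeps the full 0.05. The cost falls on non-primary BTMs. The table gives power at the strictest Holm step for an effect of 1.06 SD, which is the back-calculated figure because the documents give none. The gated rows assume that the primary effect is also 1.06 SD and that the marker correlation is 0 to 0.9.

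| Setting | at 0.05/3 | at 0.05/4 |
|---|---|---|
| Before the gate, 15 to 20 per arm | 64% to 80% | 60% to 76% |
| With the gate, 15 per arm | 51% to 63% | 48% to 59% |
| With the gate, 20 per arm | 72% to 79% | 69% to 76% |
| With the gate, 20 per arm, 4 K citrate women carried forward at no effect | about 38% to 52% | about 35% to 48% |

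With uncorrelated markers the gated power is the product of the two powers. At 15 per arm, 0.800 × 0.640 = 0.512 and 0.800 × 0.596 = 0.477. In the last row, 0.713 × 0.530 = 0.378 and 0.713 × 0.484 = 0.345. That row is the least favourable case, and the sponsor should see it before choosing.
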